2. BACKGROUND AND RATIONALE

2.1 Overview of Disease

2.1.1 *Transthyretin Amyloidosis*

Transthyretin is synthesized primarily in the liver and is secreted into the plasma as a 55 KD protein composed of 4 identical subunits of 14 KD each. A major function of TTR in the plasma is to transport retinol (vitamin A) to tissues through an association with retinol binding protein 4 (RBP4). Transthyretin amyloidosis is a rare hereditary disease caused by mutations in the TTR protein. The disease causing mutations destabilize the normal tetrameric structure of TTR causing its dissociation into free monomers and subsequent aggregation into insoluble fibril deposits. These deposits are found in multiple organs including the peripheral nervous system, GI tract and heart. They result in local damage to cells leading to a peripheral polyneuropathy (called Familial Amyloid Polyneuropathy or FAP) and a cardiomyopathy (called Familial Amyloid Cardiomyopathy or FAC).

The main clinical manifestations of FAP are progressive peripheral sensorimotor and autonomic neuropathy. Sensory neuropathy starts in the lower extremities with paresthesias and hypoesthesias of the feet, followed within a few years by motor neuropathy (Sekijima et al. 2009). Gastrointestinal symptoms, characterized by diarrhea and weight loss can also be prominent and reflect autonomic dysfunction (Falk et al. 1997; Ando et al. 2005). Death, on average, occurs within 10 years from symptom onset and is primarily due to malnutrition and cachexia, cardiac disease, sudden death or renal failure (Coelho et al. 2008). FAP can be classified into 3 stages of disease based on ambulatory status: Stage 1 – do not require assistance with ambulation; Stage 2 – require assistance with ambulation; Stage 3 – wheelchair bound (Coutinho et al. 1980). The total worldwide prevalence of FAP has been estimated at approximately 10,000 patients (Coelho et al. 2008).

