9.4 Monitoring and Recording Adverse Events

Any pre-existing conditions or signs and/or symptoms present in a patient prior to the start of the study (i.e., before informed consent) should be recorded as Medical History and not recorded as AEs unless the pre-existing condition worsened. The Investigator should always group signs and symptoms into a single term that constitutes a **single unifying diagnosis** if possible.

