10.2 Sample Size Considerations

The sample size for this study was estimated using information published from the placebo controlled Phase 3 Diflunisal trial (Berk et al. 2013), a retrospective, multinational natural history study in 283 FAP patients (Adams et al. 2015), and uncontrolled data using another TTR mRNA targeted therapeutic (Adams 2015). It is estimated that the placebo group will have a 16 point increase in the mNIS+7 score from baseline to Month 15, and the treated group will have a 6.4 point increase in mNIS+7. The standard deviation of the change from baseline in each treatment group is estimated to be 14. With 135 patients (2:1 allocation ratio) there would be at least 90% power to detect a 9.6 point difference in the change from baseline in the mNIS+7 score between the 2 groups, with a 2-sided t-test of 5% alpha, assuming that the dropout rate is approximately 25%.

For the Norfolk QOL-DN questionnaire total score, it is estimated that the placebo group will have a 13.3 point change from baseline to Month 15, the treated group will have a 2.6 point change from baseline and the standard deviation of the change from baseline in each treatment group will be 18. With 135 patients, there would be at least 80% power to detect a 10.7 point difference in the change from baseline in the Norfolk QOL total score between the 2 groups, with a 2-sided 5% alpha, assuming that the dropout rate is approximately 25%.

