3.9.2 Adverse Events

Treatment-emergent adverse events (TEAEs) are defined as adverse events that first occurred or worsened after the first dose of Study Drug. An AE with a completely missing start date will be assumed to be treatment emergent. Adverse events will be coded using Medical Dictionary for Regulatory Activities (MedDRA). The final version used will be designated in the clinical study report. For each TEAE, the severity level of the event (mild, moderate, or severe) will be determined by physician opinion. If the maximum severity of the adverse event is greater than the baseline severity, or if the onset date/time is the same as or after the date/time of the first dose of Study Drug, then the event is considered to be treatment emergent.

In the situation where change in severity (but no change in seriousness) occurs for an adverse event, study sites are instructed to enter an end date and start a new record for the adverse event. In the new record, the changed severity is to be recorded and the start date will be set to be the end date of the previous record. Data linking those records are collected in the database. Consider three scenarios:

- The first AE record occurs prior to the first dose, the second AE record occurs on or after the first dose, and the severity increases: Only the second record will be counted as treatment-emergent.
- The first AE record occurs prior to the first dose, the second AE record occurs on or after the first dose, and the severity decreases: Neither record will be counted as treatment-emergent.
- Both records occur on or after the first dose: If the AE severity on the second record is worse than the severity on the first record, then count both records as treatment-emergent. But, if the severity improves, then only count the first record as treatment-emergent.

Of note, when counting the total number of treatment-emergent events, events linked through change in severity will still be counted as separate events.

The following categories of AEs will be summarized by treatment group: all TEAEs; TEAEs leading to early discontinuation from Study Drug or from study; and serious adverse events. The percentages of patients reporting the adverse event will be summarized by MedDRA System Organ Class (SOC) and Preferred Term (PT), sorted by SOC alphabetically and then by decreasing frequency of PT within SOC.

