Summaries of related TEAEs, TEAEs by maximum severity, TEAEs during the safety treatment period, and TEAEs grouped by time from first dose to event onset (< 6 months, ≥ 6 months to < 12 months, ≥ 12 months) will also be provided.

All TEAEs will be summarized for subgroups defined by the following variables: Age, Sex, Race, Region, CM-ECHO Set, V30M TTR mutation, previous treatment with Vyndaqel® or Diflunisal, disease stage. Results will not be provided for a variable if the overwhelming majority of patients are within one level of the subgroup. Non-TEAEs reported will be flagged in the all AE listing.

A listing will be provided stating which subjects reported each preferred term. Adverse events in the following categories will be summarized separately:

- Adverse events of special interest
- Other adverse events of interest

Summary tables of the number and percentage of subjects with these adverse events will be displayed split by AE category and treatment group. TEAEs of special interest and other TEAE of interest will also be summarized for patients in the CM-ECHO Set. Statistical comparison between treatment groups will be done for AEs of special interest and other AEs of interest using the risk difference (ISIS 420915 – Placebo) and associated 95% CI.

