3.9.2.2 Other Adverse Events of Interest

The following list includes other adverse events that have been identified to be of interest:

Other AEs of interest	Definition
Coagulation abnormalities	AE with HLT: Coagulopathies
Abnormal liver function	AE within the SMQ: Drug related hepatic disorders – comprehensive search
Adverse events at the injection site	AE with HLT: Injection site reaction; or AE with HLT: Administration site reaction NEC
Flu-like symptoms	
 • AE with PT Influenza like illness; or • AE with PT Pyrexia (or Feeling hot or Body temperature increased) plus at least one of the following symptoms: 
 1. Chills 2. Myalgia 3. Arthralgia 4. Malaise 5. Fatigue 6. Headache 7. Nausea 
Note that only events that start on the day of the injection or the day after injection will be included. AEs with partial or missing dates will be handled as follows. First establish whether the event is treatment emergent. If yes, then establish if the preferred terms match the ones listed in the flu-like symptoms definition. If yes, check whether the event onset dates are within the specified time frame. If at this stage, onset date is missing or partially missing, the event will be considered to have started within the required time frame.

CNS disorders	AE with SOC: Nervous system disorders
Haemorrhages	AE within the SMQ: Haemorrhages
Complement activation	AE within SMQ: Hypersensitivity

Other AEs of interest	Definition
Reduced thyroxine	AE within SMQ: Hypothyroidism

For haemorrhages results will be further classified by type of event, using the following categories: actual bleeds, hematomas/subdermal bleeds, investigations SOC (test result), and DIC, TTP. Events classified as actual bleeds or hematomas/subdermal bleeds will be further categorized by whether the event occurred at injection site or not at injection site.

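### SAP 3.9.2.2 defines the 'CNS disorders' category as the whole Nervous system disorders SOC, so AEs of worsening FAP enter its risk difference and would bias it in the drug's favour if the drug slows neuropathy.

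*SAP*

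**What the plan says.** The table in SAP 3.9.2.2 has a row labelled 'CNS disorders' whose complete definition is "AE with SOC: Nervous system disorders". It is the only row in the tables of 3.9.2.1 and 3.9.2.2 defined by an entire SOC; the others use high level terms, preferred terms or SMQs. Haemorrhages are broken down further by type of event. 'CNS disorders' is not.

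SAP 3.9.2 attaches an estimate to the row: "Statistical comparison between treatment groups will be done for AEs of special interest and other AEs of interest using the risk difference", drug minus placebo, with a 95% CI. The other events of interest are also summarised for the CM-ECHO Set.

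Three further statements determine what enters the row:

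- Protocol 2.1.1, on the disease: "The main clinical manifestations of FAP are progressive peripheral sensorimotor and autonomic neuropathy".
- Protocol 9.4, on pre-existing signs and symptoms: they are "not recorded as AEs unless the pre-existing condition worsened".
- SAP 3.9.2, on treatment-emergent events: "adverse events that first occurred or worsened after the first dose of Study Drug".

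Neither document exempts progression of FAP from AE recording or removes peripheral or autonomic terms from this row.

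**The concern.** The label names the central nervous system, but the rule takes the nervous system as a whole. In most trials that would be a loose label. Here the trial disease is itself a disorder of the peripheral and autonomic nerves, and the primary endpoint measures its progression. Worsening that is reported as an AE and coded to this SOC is counted as a 'CNS' event.

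The likely direction follows from the planning assumptions. Protocol 10.2 expects that "the placebo group will have a 16 point increase in the mNIS+7 score from baseline to Month 15" and that "the treated group will have a 6.4 point increase in mNIS+7". If that holds, progression-related nervous system AEs should be more frequent on placebo, and the drug-minus-placebo difference moves down. The drug would look safer for the central nervous system because it works on peripheral nerves. If the drug does not work, a similar background in both arms still shrinks the difference and widens its interval. At stake is the only planned between-arm estimate, with an interval, for a category named for CNS events.

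**Working it through.** The plan states no rate, power or margin for this category, so there is no figure of its own to reproduce.

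**Inputs from the documents.** About 90 patients on drug and 45 on placebo (Protocol 3.3); comparison by risk difference, drug minus placebo, with 95% CI (SAP 3.9.2).

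**Assumed inputs.** True central AEs in 10% on drug and 5% on placebo. Background AEs from neuropathy varied from 15% to 40% on drug and from 20% to 50% on placebo. Central and background AEs independent within each arm. None of these rates is in the documents.

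**Formulas.**

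- Proportion with any AE in the SOC, per arm: 1 - (1 - background)(1 - central).
- Risk difference (RD): drug minus placebo.
- Wald half-width: 1.96 × √[p_d(1 - p_d)/90 + p_p(1 - p_p)/45].

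**Central terms only.** RD = 10 - 5 = +5.0 points. Half-width = 1.96 × √(0.10×0.90/90 + 0.05×0.95/45) = 8.9 points, so the interval is -3.9 to 13.9.

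**Whole SOC, one case in full.** With background 25% on drug and 40% on placebo:

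- drug: 1 - 0.75×0.90 = 32.5%
- placebo: 1 - 0.60×0.95 = 43.0%
- RD = -10.5 points, half-width 17.4

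**Whole SOC, range** (true central difference +5.0 throughout):

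| Background, drug | Background, placebo | SOC, drug | SOC, placebo | RD (points) | Half-width |
|---|---|---|---|---|---|
| 40% | 40% | 46.0% | 43.0% | +3.0 | 17.8 |
| 15% | 20% | 23.5% | 24.0% | -0.5 | 15.3 |
| 25% | 40% | 32.5% | 43.0% | -10.5 | 17.4 |
| 30% | 50% | 37.0% | 52.5% | -15.5 | 17.7 |

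**How much background difference changes the sign.** RD is zero when (1 - background on drug)/(1 - background on placebo) = 0.95/0.90 = 1.056. With 40% on placebo, the background on drug must be 1 - 0.60×1.056 = 36.7%, or 3.3 points lower. With 20% on placebo it must be 1 - 0.80×1.056 = 15.6%, or 4.4 points lower.

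**A larger central effect, 20% against 5%.** Central terms only: +15.0 (4.6 to 25.4). Whole SOC:

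- equal backgrounds of 20%: +12.0 (-3.9 to 27.9)
- equal backgrounds of 40%: +9.0 (-8.8 to 26.8)
- 20% on drug against 40% on placebo: -7.0 (-24.5 to 10.5)

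For an effect of this size, the equal-background cases show that dilution alone can move an interval from excluding zero to including it.

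**The case against.** The strongest reply is that little depends on this row. SAP 3.9.2 tabulates all TEAEs, serious events and events leading to discontinuation by SOC and preferred term in each arm, and lists which subjects reported each preferred term. Central terms are therefore visible. Related TEAEs are also summarised, and Protocol 9.4.3.1 classes an event readily explained by the underlying condition as not related, so that view should carry less FAP background. The category is not one of the events of special interest in SAP 3.9.2.1, and no test or stopping rule uses it. Protocol 2.2 says that drugs of this class do not cross the blood-brain barrier. The fatal intracranial bleed in the amendment summary belongs with haemorrhages and thrombocytopenia, which have their own rows. All this stands and limits the consequence. It does not make the row measure what it is named for.

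A second reply is that the rates are invented. That is so. A difference in mNIS+7 does not establish a difference in AE rates. Sites are told to group signs and symptoms into one unifying diagnosis, and some FAP manifestations, such as gastrointestinal ones, would be coded elsewhere. Independence is also an assumption. The mismatch between label and rule needs no rate, but the size of the bias does.

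A third reply is that a central-only row may still be inconclusive: in the +5 point case its interval includes zero. This is correct. The narrower definition removes a bias and roughly halves the interval's width; it does not supply power.

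A fourth reply is that excluding sensory and peripheral terms could hide neurotoxicity of the drug itself. This is a good point, and it shapes the fix.

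**Conclusion.** The point holds as a mismatch between label and definition. The bias in one planned safety comparison has a direction that the sponsor's own efficacy assumption predicts. Its size cannot be known from the documents. Under the assumed, independent rates above, a true excess of 5 points appears as anything from +3.0 to -15.5, with a half-width of about 15 to 18 points instead of about 9.

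A reader might infer that a CNS safety signal would be lost, or that the plan leaves CNS safety unassessed. The documents do not support that. The SOC/PT tables, the related-event summary and the preferred-term listing still show central terms by arm, though only descriptively. A reader might also take the sign reversal as a forecast; it illustrates assumed rates. The effect is limited to this summary row and its CM-ECHO repeat. Primary efficacy is untouched. The change is worth making because the row would otherwise report a mixture under a CNS label.

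**What to change.** In SAP 3.9.2.2, before unblinding, split the Nervous system disorders SOC by a fixed term list into two rows:

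- (a) central nervous system terms, labelled 'CNS disorders';
- (b) peripheral, sensory and autonomic terms, under a neutral label. A label such as 'possible disease progression' should be avoided, because it would prejudge events that might be drug neurotoxicity.

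Report the risk difference with 95% CI for (a), for (b), and for the whole SOC labelled 'Nervous system disorders'. Do the same split in the CM-ECHO summary. Nothing is then dropped, and each row measures what its name says.

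The cost is SAP wording and a term list, with no new data. The small downside is that terms such as dizziness, syncope and paraesthesia do not place themselves and need a decision made while still blinded.

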3.9.2.3 Local Cutaneous Reactions at Injection Site (LCRIS)

The following MedDRA preferred terms are determined by the Sponsor's Pharmacovigilance personnel to represent the local cutaneous reaction at the injection site:

- Injection site erythema
- Injection site swelling
- Injection site pruritus
- Injection site pain
- Injection site tenderness

Only events that start on the day of injection and persist for at least two days, i.e. event onset date on the day of injection and resolution date not on the day of injection or the day after the injection, will be included. Events with onset date on the day of injection and missing resolution date will also be included. AEs with partial or missing dates will be handled as follows. First establish whether the event is treatment emergent. If yes, then establish if the preferred terms match the ones listed in the LCRIS definition. If yes, check whether the event onset dates are within the specified time frame. If at this stage, onset date is missing or partially missing, the event will be considered to have started within the required time frame. The number and percent of patients in each treatment group experiencing LCRIS will be tabulated.

Percentage of injections leading to local cutaneous reactions at the injection site will also be summarized. Percentage of injections leading to local cutaneous reactions will be calculated for each patient as $(A/B)*100$, where A is the number of injections with a local cutaneous reaction at the injection site, and B is the total number of injections.

3.9.2.4 Flu-Like Reactions

The following MedDRA preferred terms are determined by the Sponsor's Pharmacovigilance personnel to be the flu-like reactions:

- Influenza like illness
- Pyrexia (or Feeling hot or Body temperature increased) plus at least two of the following symptoms:
 1. Chills
 2. Myalgia
 3. Arthralgia

Only events that start on the day of injection or the day after injection will be included. AEs with partial or missing dates will be handled as follows. First establish whether the event is treatment emergent. If yes, then establish if the preferred terms match the ones listed in the flu-like reactions definition. If yes, check whether the event onset dates are within the specified time frame. If at this stage, onset date is missing or partially missing, the event will be considered to have started within the required time frame.

The number and percent of patients in each treatment experiencing flu-like reactions will be tabulated.

Percentage of injections leading to flu-like reactions will also be summarized. Percentage of injections leading to flu-like reactions will be calculated for each patient as $(A/B)*100$, where A is the number of injections associated with a flu-like reaction, and B is the total number of injections.

3.9.3 Vital Signs, Weight, and Physical Examination Findings

Vital signs include systolic and diastolic blood pressure, pulse, respiratory rate, and temperature. Weight will also be analyzed. Absolute values at each visit, change and percent change from baseline to each visit in vital signs and weight will be summarized by treatment group. No statistical comparisons between treatments will be performed for this summary.

All vital signs and weight will be listed. Physical examination findings will also be listed.

3.9.4 Laboratory Measurements

Laboratory tests to ensure patient safety include chemistry panel, complete blood count with differential, thyroid panel, coagulation panel, immunogenicity, inflammatory panel, complement, and urinalysis. Absolute values, change and percent change from baseline will be summarized by visit and treatment group for continuous laboratory tests. No statistical comparisons between treatments will be conducted for these summaries. The mean value (and associated standard error) will be plotted by treatment group over visits for the following laboratory parameters: platelets, eGFR, urine A/C ratio, and urine P/C ratio.

All laboratory test results will be listed. Separate listings will be provided for local and central labs. The central lab listing will be based on the ADaM dataset and will include all central lab records. The local lab listing will be based on the SDTM dataset. A separate listing for platelets will be provided that includes assessment from both the local and central labs. A separate listing will contain only values outside of normal ranges. The number and percent of patients that stopped treatment because they met a protocol-defined stopping rules for liver function, renal function, or platelet counts will be tabulated by treatment group.

Additional investigation of hepatobiliary laboratory assessments, platelet counts and renal parameters will be performed, and are detailed in the sections below. In this investigation confirmed laboratory values will also be summarized.

A confirmed laboratory value is based on consecutive lab values within 7 days. If that value is in the same or worse category the initial value is confirmed. If the consecutive value is in a better category then the initial value is confirmed using consecutive value category. If there is no retest within 7 days then the initial value is presumed confirmed. If there are multiple results on the same day (no matter from the same lab vendor or different lab vendors), then the worst value will be utilized in the analysis.

3.9.4.1 Hepatobiliary Laboratory abnormalities

The number and percentage of patients falling in each of the following categories based on post-baseline assessments will be provided:

- ALT \geq 3xULN and total bilirubin \geq 2xULN
- Confirmed ALT \geq 3xULN and confirmed total bilirubin \geq 2xULN
- ALT \geq 3xULN and international normalized ratio $>$ 1.5
- ALT \geq 3xULN and total bilirubin \geq 2xULN and ALP $<$ 2xULN
- Hepatocellular injury
- Hepatocellular injury and total bilirubin \geq 2xULN
- ALT \geq 3xULN
- ALT \geq 5xULN
- ALT \geq 8xULN
- ALT \geq 10xULN
- ALT \geq 20xULN
- Confirmed ALT \geq 3xULN
- Confirmed ALT \geq 5xULN
- Confirmed ALT \geq 8xULN
- Confirmed ALT \geq 10xULN
- Confirmed ALT \geq 20xULN
- ALT \geq 3xULN - $<$ 5xULN
- ALT \geq 5xULN - $<$ 10xULN
- ALT \geq 10xULN - $<$ 20xULN
- Total bilirubin \geq 2xULN
- ALP \geq 2xULN and baseline ALP $<$ 2xULN or baseline ALP missing
- ALT \geq 3x ULN or ALT \geq 2 x baseline
- Confirmed ALT \geq 3x ULN or confirmed ALT \geq 2 x baseline

For patients that had ALT elevation \geq 3 xULN, the time from first dose to first ALT elevation \geq 3 xULN will be summarized using the following descriptive statistics: mean, standard deviation, median, P25, P75, and minimum and maximum.

Shift tables from baseline for ALT, AST, and total bilirubin based on peak (maximum) and confirmed peak category will also be provided. Categories for the ALT and AST shift tables will be $<$ 3 x ULN, \geq 3

x ULN to < 5 x ULN, ≥ 5 x ULN to < 8 x ULN, and ≥ 8 x ULN. Categories for the total bilirubin shift table will be < 2 x ULN and ≥ 2 x ULN.

A hepatocellular injury event is defined as $(ALT/ALT\ ULN)/(ALP/ALP\ ULN) \geq 5$ and $ALT \geq 3xULN$, with the ALT and ALP assessments done on the same day. The categories listed above will also be analyzed using AST in place of ALT. For these analyses the definition of hepatocellular injury will not be changed to depend on AST.

